3.3 Exploratory Objectives

- (1) **Objective:** For Part I, to evaluate the ORR and PFS of MK-1454 as assessed by investigator when used as monotherapy and as combination therapy with pembrolizumab. In solid tumors, assessment will be based on RECIST 1.1 and irRECIST. ORR and PFS as assessed according to RECIST v1.1 modified to follow a maximum of 10 total target lesions with a maximum of 5 target lesions per organ. In lymphomas, assessment will be based on the IWG revised response criteria [1]. For subjects with CTCL, response assessment will be based on the Global Response Score (see Table 22) [2].
- (2) **Objective**: Separately for each tumor type in Part II*, evaluate PFS of MK-1454 at the preliminary RP2D in combination with pembrolizumab as assessed by the investigator by RECIST 1.1 modified to follow a maximum of 10 total target lesions and a maximum of 5 target lesions per organ.
- (3) **Objective**: In Parts I and II, to evaluate the effect of the study intervention on lesions not treated with IT injections, as assessed by investigator. The measurements of effect will include the ORR for noninjected lesions and the maximal reduction in the sum of diameters of noninjected target lesions, as described in itRECIST [3].
- (4) **Objective**: In Part I, to evaluate overall survival (OS) of subjects treated with MK-1454 both as monotherapy and as combination therapy with pembrolizumab.

^{*} Note: Efficacy analyses for each Part II expansion cohort will pool Part I subjects who meet the inclusion criteria for the respective Part II tumor type and received the same dose level of MK-1454 in combination with pembrolizumab.

Protocol/Amendment No.: 001-08

(5) **Objective**: Separately for each tumor type in Part II*, to evaluate OS of MK-1454 at the preliminary RP2D in combination with pembrolizumab. *Note: Efficacy analyses for each Part II expansion cohort will pool Part I subjects who meet the inclusion criteria for the respective Part II tumor type and received the same dose level of MK-1454 in combination with pembrolizumab.

- (6) **Objective**: To identify molecular (genomic, metabolic and/or proteomic) biomarkers that may be indicative of clinical response/resistance, safety, pharmacodynamic activity, and/or the mechanism of action of MK-1454 as monotherapy and in combination with pembrolizumab and other treatments.
 - a. To investigate TNF- α and other cytokines that may correlate with tumor response.

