Proteomics and immunohistochemistry (IHC) using blood or tumor: Tumor and blood samples from this study may undergo proteomic analyses (eg, PD-L1, CD8, CD4 IHC). PD-L1 protein level in tumor sections, assessed by IHC, has been shown to correlate with response to pembrolizumab in patients with NSCLC, and an in vitro diagnostic device has been developed for use with pembrolizumab in NSCLC. Preliminary data indicates that this association may also be true in additional cancer types (ie, TNBC, head and neck cancer, and gastric cancer). Additional tumor or blood-derived proteins may also correlate with response to pembrolizumab. Therefore, tumor tissue may be subjected to proteomic analyses using a variety of platforms that could include but are not limited to immunoassays, liquid chromatography/mass spectrometry. This approach could identify novel protein biomarkers that could aid in patient selection for MK-1454 therapy.

Other Blood-derived Biomarkers: In addition to expression within the tumor tissue, tumor-derived proteins (eg, PD-L1) or tumor-derived DNA can be shed from tumor and released into the blood. In the case of proteins, enzyme-linked immunosorbent assay can measure such proteins in serum and plasma and correlate this expression with response to pembrolizumab therapy, as well as levels of protein in the tumor. Deoxynucleic acid can be analyzed using next generation sequencing or polymerase chain reaction-based technologies. Advantages to this method are that blood is a less invasive compartment from which tumor-derived protein or nucleic acid biomarkers may be measured.

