5.2.5.2 Timing of MK-1454 Dose Administration in Part II - Expansion Cohorts

In Cohorts A and B, MK-1454 IT will be administered on Day 1, Day 8, and Day 15 in each 21-day cycle for Cycles 1 and 2. Beginning with Cycle 3, MK-1454 will be administered on Day 1 of each 21-day cycle.

Cohort C will initiate MK-1454 visceral IT treatment at the dose and frequency established as the RP2D from Arm 3.

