5.2.5.3 Timing of Pembrolizumab Administration

Pembrolizumab 200 mg will be administered as an IV infusion on Day 1 of each 21-day cycle, in all combination treatment arms in Part I and Part II.

Protocol/Amendment No.: 001-08

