Bone Marrow Biopsy/ Aspirate (Lymphoma Subjects Only [excluding CTCL subjects])	X	X	Must be performed if not previously done within 8 weeks prior to Screening with negative results. For a crossover subject, a repeat bone marrow biopsy at screening is required when the subject crosses over into Arm 2 if bone marrow biopsy results were negative at Screening in Arm 1.					
Safety Assessments and Procedures			See Procedures Manual for collection and management of tissue samples					
Full Physical Examination	X	X						
Height	X							
Weight	X	X						
12-lead Electrocardiogram (ECG)	X	X	ECG will be obtained within 7 days prior to MK-1454 IT administration on C1D1.					
Vital Signs	X	X	Temperature, pulse, respiratory rate, blood pressure, and oxygen (O ₂) saturation					
ECOG Performance Status	X	X	Additional ECOG assessments may be performed as clinically indicated.					
Tumor Markers	X	X						
CBC with Differential	X	X	Perform all screening clinical laboratory tests within 7 days prior to treatment					
PT/INR and PTT or aPTT	X	X	initiation. Tests performed prior to the subject signing consent as part of routine					
Chemistry Panel	X	X	clinical management are acceptable in lieu of a screening test, if the test is					
LDH, GGT	X	X	performed within the specified time frame. Specific tumor markers (eg, CEA,					
Lipase and Amylase	X	X	CA-125, CA-19-9, and alpha fetoprotein) are to be obtained as clinically					
Urinalysis	X	X	indicated.					
Thyroid Function (TSH, T3, FT3, T4, FT4)	X	X						
Pregnancy Test for WOCBP– Urine or Serum hCG	X	X	Perform within 7 days prior to treatment initiation. If a urine pregnancy test cannot be confirmed as negative, a serum pregnancy test is required. Perform pregnancy testing per local regulations.					
Hepatitis B and C	X		Include HCV antibody or HCV RNA (qualitative) and HBsAg. HIV by history is acceptable for exclusion, unless testing is required by local regulations.					
Laboratory Procedures/Assessments: An CENTRAL laboratory	alysis performe	d by	See Procedures Manual for collection and management of tissue samples.					
Serum for Cytokine Panel and C-Reactive Protein (CRP) for MK-1454 Pharmacodynamics	X	X	Blood samples for serum cytokine panels and CRP taken at Screening should be obtained either both in the morning (8 AM to 12 PM) or both in the afternoon (1 PM to 5 PM). Collect with the samples for MK-1454 PK, when feasible.					
Blood for Plasma Biomarker Analysis	X	X						

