Blood for Serum Biomarker Analysis	X	X						
Tumor Tissue Biopsy ^a	Xa	Xa						

Protocol/Amendment No.: 001-08

	Initial	Crossover	Notes
Scheduled Day	Screening	Screening	Screening and Day 1 cannot be on the same day.
	-28 to -1	-28 to -1	

aPTT = activated partial thromboplastin time; CBC = complete blood count; hCG = Beta-human chorionic gonadotropin; CRP = C-reactive protein; CT = computed tomography; CTCL = cutaneous T-cell lymphoma; ECOG = Eastern Cooperative Oncology Group; FBR = future biomedical research; GGT = gamma glutamyl transferase; HIV = human immunodeficiency virus; HNSCC = Head and Neck Squamous Cell Carcinoma; HPV = human papillomavirus; INR = international normalized ratio; IT = intratumoral; IWG = International Working Group; LDH = lactate dehydrogenase; MRI = magnetic resonance imaging; NASBA = nucleic acid sequence-based amplification; PET = positron emission tomography; PT = prothrombin time; PTT = partial thromboplastin time; RNA = ribonucleic acid; RECIST v1.1 = Response Evaluation Criteria In Solid Tumors, version 1.1; irRECIST = immune-related RECIST; (F)T3 = (free) triiodothyronine; (F)T4 = (free) thyroxine; TSH = thyroid-stimulating hormone; WOCBP = women of childbearing potential.

a.) All subjects will be required to provide a sample biopsy of the tumor to be injected with MK-1454 and a sample biopsy from a distant, discrete noninjected site (at least 2 biopsies at each site) at Screening, unless deemed medically unsafe by the investigator. This predose tumor biopsy at Screening will be performed on both the tumor lesion that is intended for treatment with IT administration of MK-1454, as well as on the distant lesion that is not intended for IT administration with MK-1454. For the tumor lesion intended for treatment with IT administration of MK-1454, the sample will be obtained by either punch biopsy for cutaneous lesions, or ultrasound guided biopsy for subcutaneous lesions, or cross-sectional image-guided biopsy for visceral and deeper tumor lesions. For distant, discrete tumor lesions that are not intended for IT administration with MK-1454, the sample biopsy will be obtained by punch biopsy for cutaneous lesions, ultrasound guided biopsy for subcutaneous lesions/visceral lesions, or cross-sectional image-guided biopsy, such as CT-guided biopsy, for visceral and deeper tumor lesions. Method of biopsy will be per guidance of the investigator as well as discussion with the Sponsor.

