Urinalysis	X	X			X			X			X	testing must be performed within 72 h prior to dosing when scheduled. Does not need to be repeated on C1D1 if
Lipase and Amylase	X	X			X			X			X	screening labs were done within 72 hours of C1D1.
Pregnancy Test for WOCBP – Urine or Serum hCG	X	X										Required within 24 h prior to first dose of study medication. Does not need to be repeated if screening test was done within 24 hours of C1D1. If a urine pregnancy test cannot be confirmed as negative, a serum pregnancy test is required. Pregnancy testing must be done as required by local regulation. Where local regulations require monthly pregnancy testing per CTFG guidelines, see Appendix 12.5.
Thyroid Function (TSH, T3, FT3, T4, FT4)	X	X						X			X	Required within 72 hours prior to Day 1 of C1, C3, C5, C7, C9, C11, and at every other subsequent treatment cycle. Does not need to be repeated on C1D1 if screening labs were done within 72 hours of C1D1.
HIV, Hepatitis B and C screen (per site SOP)	X											Include HCV antibody or HCV RNA (qualitative) and HBsAg.

MK-1454-001-08 Final Protocol 27-Jul-2021 Confidential

Protocol/Amendment No.: 001-08

Trial Period	Screening		Treatment Phase MK-1454 Cycle = COI then Q3W; or Q3W Pembrolizumab Cycle = 21 Days Cycle 4									
			~ .		_				~		and	
Cycle	20.4 4		Cycle		1	Cycle 2		_	Cyc		Beyond	Notes
Scheduling Day Scheduled Window	-28 to -1	1	8	15	1	8	15	1	8	15	1	
Scheduled Window	Lab	_	±3 ±3 ±3 ±3 ±3 ±3 ±3 ±3								See Procedures Manual for Collection and Management of Samples.	
Serum for Cytokine Panel and CRP for MK-1454 Pharmacodynamics ^b	X	X			X						X·	Cytokine and CRP samples should be obtained at Screening, and predose on C1D1, C2D1 and C5D1, either both in the morning (8 AM to 12 PM) or both in the afternoon (1 PM to 5 PM). Postdose serum samples for cytokine panels and CRP will be collected on C1D1, C2D1, and C5D1. Postdose samples will be collected at 4 h (±15 min) and 6 h (±15 min) after MK-1454 administration. Collect samples at the same time as for MK-1454 PK when feasible.
Plasma MK-1454 PK ^b		X			X						X	Collect predose samples 1-8 h before MK-1454 administration on C1D1 and C2D1. Collect postdose samples on C1D1 and C2D1 at the following time points: end of IT injection (up to +15 min), 0.5 h (±15 min), 1 h (±15 min), 1.5 h (±15 min), 4 h (±15 min), and 6 h (±15 min). Collect samples at the same time as for cytokines and CRP, and for pembrolizumab PK, when feasible.

Protocol/Amendment No.: 001-08

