Trial Period	Screening			MK-1	454 C Pem	ycle =	CCI	ent Ph th Cyclo		W; or Q3V Days		
Cycle	Screening		Cycle	1	(Cycle 2	2		Cycle 4 and Beyond		and	Notes
Scheduling Day	-28 to -1	1	8	15	1	8	15	1	8	15	1	
Scheduled Window		±3	±3	±3	±3	±3	±3	±3	±3	±3	±3	
Serum for Pembrolizumab PK		X			X						X	Collect samples predose 0 to 4 h before pembrolizumab IV infusion on C1D1, C2D1, C4D1, and on Day 1 of every 4
Serum for ADA		X			X						X	cycles thereafter (ie, C8, C12, etc.). Collect pembrolizumab and MK-1454 PK samples together, when feasible.
Blood for Plasma Biomarker Analysis					X						X	Collect prior to MK-1454 administration (Arm 1) and prior to pembrolizumab administration (Arm 2) on C2D1 and C5D1.
Blood for Serum Biomarker Analysis					X						X	
Blood for RNA Analysis		X										Collect predose 0-4 h before MK-1454 administration on C1D1 Collect postdose 6 h (±15 min) after MK-1454 administration on C1D1.
Blood for Genetic Analysis ^c		X										Collect prior to treatment.
Tumor Tissue Biopsy ^d	Х				X			X				For the tumor lesion that is treated with IT administration of MK-1454, collect predose tumor biopsy on the same day as treatment prior to IT administration of MK-1454, or up to 5 days prior to treatment on C2D1 and on C3D1 (optional). If available, biopsy of a distant, discrete, noninjected site may be performed up to 5 days before treatment of the injected lesion.

AE = adverse event; aPTT = activated partial thromboplastin time; CBC = complete blood count; CRP = C-reactive protein; CT = computed tomography; CTCL = cutaneous Tcell lymphoma; ECOG = Eastern Cooperative Oncology Group; EOT = end of treatment; FBR = future biomedical research; (F)T3 = (free) triiodothyronine; (F)T4 = (free) thyroxine; GGT = gamma glutamyl transferase; hCG = human chorionic gonadotropin; HCV = hepatitis C virus; HIV = human immunodeficiency virus; HNSCC = Head and Neck Squamous Cell Carcinoma; HPV = human papillomavirus; INR = international normalized ratio; irRECIST = immune-related RECIST; ISCL = International Society for Cutaneous Lymphomas; IT = intratumoral; LDH = lactate dehydrogenase; MRI = magnetic resonance imaging; NASBA = nucleic acid sequence-based amplification; PET = positron emission tomography; PK = pharmacokinetics; PT = prothrombin time; PTT = partial thromboplastin time; RECIST v1.1 = Response Evaluation Criteria In Solid Tumors, version 1.1; RNA = ribonucleic acid; TSH = thyroid-stimulating hormone; WOCBP = women of childbearing potential.

087V73

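### In Part II the general plasma and serum biomarker samples have no pretreatment draw, so analytes measured only in those samples have no baseline in Cohorts A to C

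*Combined protocol and SAP*

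**What the plan says.** Exploratory objective 6 (section 3.3) is "To identify molecular (genomic, metabolic and/or proteomic) biomarkers that may be indicative of clinical response/resistance", and also covers safety, pharmacodynamic activity and mechanism of action. Section 4.2.3.5.1, under other blood-derived biomarkers, describes proteins and DNA shed from the tumor into blood. It says that an immunoassay can "measure such proteins in serum and plasma and correlate this expression with response to pembrolizumab therapy".

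In Part I the screening table (6.1.1) marks "Blood for Plasma Biomarker Analysis" and the matching serum row at both initial and crossover screening. The Part I treatment tables then add C2D1 and C5D1.

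In Part II one table (6.2.1) covers both screening and treatment. Its plasma and serum biomarker rows are marked only at C2D1 and in the column for Cycle 4 and beyond. The note says "Collect prior to MK-1454 administration (Arm 1) and prior to pembrolizumab administration (Arm 2) on C2D1 and C5D1". Section 6.2.2 adds an end-of-treatment sample for both rows.

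**The concern.** A marker proposed as a baseline correlate of response has to be measured before treatment, and a pharmacodynamic change needs a pretreatment value to be measured from. In Part II the earliest value from the general plasma and serum samples is already affected by treatment. If such a marker differs between responders and nonresponders at C2D1, the data cannot show whether the difference existed beforehand or arose during Cycle 1. Part II is where response at the recommended dose is estimated by tumor type, so these are subjects in whom such associations would naturally be examined.

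The note keeps the Part I arm labels, which suggests that the Part I treatment-period row was reused without the separate screening row. The documents give no reason for the missing draw, so this remains an inference.

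**Working it through.** There is no sample-size or power figure to reproduce. The check compares the schedules and counts doses.

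**Step 1: pretreatment samples by type** (sections 6.1.1 and 6.1.2 for Arms 1 and 2; 6.2.1 and 6.2.2 for Part II).

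| Sample | Part I, before treatment | Part II, before treatment | Part II, afterwards |
|---|---|---|---|
| General plasma biomarker | Screening | none | C2D1, C5D1, end of treatment |
| General serum biomarker | Screening | none | C2D1, C5D1, end of treatment |
| Serum cytokines and CRP | Screening, C1D1 predose | Screening, C1D1 predose | C1D1 postdose, C2D1, C5D1 |
| Blood RNA | C1D1, before MK-1454 | C1D1, before MK-1454 | C1D1, 6 h after MK-1454 |
| Germline genetics | C1D1 | C1D1 | none needed |
| Tumor biopsy, injected lesion | Screening | Screening | C2D1; C3D1 optional |

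The cytokine note in 6.2.1 reads "Cytokine and CRP samples should be obtained at Screening, and predose on C1D1, C2D1 and C5D1", so that row was given its screening visit in Part II. For the two general rows the column marks and the written note agree, so the finding does not depend on how the table is laid out.

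**Step 2: treatment received before C2D1.**
- Pembrolizumab (5.2.5.3): "Pembrolizumab 200 mg will be administered as an IV infusion on Day 1 of each 21-day cycle". One infusion, on C1D1, in every cohort.
- MK-1454 in Cohorts A and B (5.2.5.2): "MK-1454 IT will be administered on Day 1, Day 8, and Day 15 in each 21-day cycle for Cycles 1 and 2". Three injections, on Days 1, 8 and 15 of Cycle 1.
- MK-1454 in Cohort C: the frequency is still to be determined in Table 8, so no count is given.

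**Step 3: subjects affected.** 30 (A) + 30 (B) + 60 (C) = 120 (section 8.9.2). As scheduled, 0 of about 120 have a pretreatment general plasma or serum sample. In Part I the sample is scheduled for all of about 115 subjects (section 8.9.1).

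**Step 4: whether later samples can substitute.** C2D1 falls 21 days after first dose and C5D1 falls 4 × 21 = 84 days after it. The first scan is at 9 × 7 = 63 days. The C5D1 minus C2D1 difference is therefore a change within treatment. It is seen only in subjects still treated after the first scheduled response assessment.

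**Step 5: whether other predose tubes are surely pretreatment.** MK-1454 follows the end of the pembrolizumab infusion by 0.5 to 4 h.
- RNA is drawn 0 to 4 h before MK-1454, so it could be drawn up to 4 − 0 = 4 h after pembrolizumab ends.
- MK-1454 PK plasma is drawn 1 to 8 h before MK-1454, so it could be drawn up to 4 − 1 = 3 h after pembrolizumab ends.
- Serum for pembrolizumab PK and antidrug antibodies is drawn 0 to 4 h before the infusion, so it is pretreatment on C1D1.

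**The case against.** A reader might infer that no expansion subject has a baseline for the blood-biomarker objective, or that Part II subjects cannot contribute to it. The documents do not support either reading. Objective 6a (TNF-α and other cytokines) has two pretreatment serum time points. Objective 6c (the STING polymorphism) has pretreatment blood. Objective 6b names circulating blood cells and tumor tissue, for which Part II has the C1D1 RNA sample and a screening biopsy. The general rows themselves supply values at C2D1, C5D1 and end of treatment, which can be related to response as on-treatment measures.

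A reader might also infer harm from pooling matching Part I subjects into the Part II sets. That rule (section 8.6.1) concerns efficacy analyses, and nothing extends it to biomarkers.

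It is fair to add that the text on shed proteins and DNA is permissive. No endpoint or change-from-baseline analysis is specified for these samples, and exploratory methods are left to a supplemental SAP that is not available here. Collection details sit in a Procedures Manual, also not available. Without a control group, a baseline value would not separate predictive from prognostic markers.

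Remaining serum and plasma, including the pretreatment pembrolizumab PK serum, may be stored for future research. That depends on optional consent, and section 4.2.3.6 reserves such work for questions outside the protocol, so it is only a partial remedy.

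These arguments limit the size of the point. They do not remove the gap, because the schedule as written gives the two general rows no pretreatment value.

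**Conclusion.** The point holds for the two general rows and no further. If 6.2.1 is followed as written, analytes measured only in those samples have on-treatment and end-of-treatment values but no baseline, in up to about 120 subjects across Cohorts A to C. Shed proteins and tumor-derived DNA are the examples that section 4.2.3.5.1 offers. For such analytes, baseline association with response and change from baseline cannot be estimated in Part II.

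This assumes that the Procedures Manual adds no earlier draw, and that the analytes are not also measured in the cytokine panel or another pretreatment tube. The objective is exploratory, and no primary or secondary analysis is affected. The point ranks as a cheap improvement.

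**What to change.** In 6.2.1, add an X to the plasma and serum biomarker rows at Screening, or at C1D1 before the pembrolizumab infusion. If C1D1 is chosen, the draw should be timed to pembrolizumab and not to MK-1454, because MK-1454 is given second. Replace the Arm 1 and Arm 2 note with wording such as: *Draw at Screening (or C1D1) and again on C2D1 and C5D1, each time before any pembrolizumab due that day.*

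The cost is one plasma and one serum tube at a scheduled blood draw, plus assays and a schedule edit. The change helps only subjects not yet treated. Cohort C (up to 60 subjects) is planned to start after Cohorts A and B.

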7.0 TRIAL PROCEDURES

7.1 Trial Procedures

The Schedule of Activities - Section 6.0 summarizes the trial procedures to be performed at each visit. Individual trial procedures are described in detail below. It may be necessary to perform these procedures at unscheduled time points if deemed clinically necessary by the investigator.

Furthermore, additional evaluations/testing may be deemed necessary by the investigator and or the Sponsor for reasons related to subject safety. In some cases, such evaluation/testing may be potentially sensitive in nature (e.g., HIV, Hepatitis C, etc.), and thus local regulations may require that additional informed consent be obtained from the subject. In these cases, such evaluations/testing will be performed in accordance with those regulations.

7.1.1 Administrative Procedures

7.1.1.1 Informed Consent

The investigator or qualified designee must obtain documented consent from each potential subject or each subject's legally acceptable representative prior to participating in a clinical trial or FBR. If there are changes to the participant's status during the study (eg, health or age of majority requirements), the investigator or medically qualified designee must ensure the appropriate documented informed consent is in place.

